We will conduct a randomized controlled trial (RCT) of VR non-opioid management vs. a control “sham” intervention for a broad and representative group of medical and surgical patients with pain. Hospitalized patients will receive specialized VR interventions, administered via Samsung Gear headsets, to manage breakthrough pain. Control patients will view content on the in-room Health and Wellness television channel. We will follow patients throughout the course of their hospitalization and monitor outcomes during and after their stays. In addition, we will measure endocrine markers of stress as an optional procedure. Our multidisciplinary team of experts in VR, digital health science, mental health, and pain management will test an intervention that, if effective, could be used in resource-limited environments and serve as an adjunct for patients receiving opioids.

Specific Aims and Hypotheses:

The proposed RCT has the following aims:

1. Assess the relative benefits of using VR versus a control intervention for pain management – including pain scores, usage of pain medication, amount of time between pain medication requests, and complications from opioid pain medication – in a large cohort of hospitalized medical and surgical patients with pain.
2. Assess other characteristics of the hospital stay potentially affected by use of VR usage, including length of stay (LOS), and readmissions.
3. Assess patient satisfaction with general care and pain management following VR usage.

We hypothesize the following regarding these aims:

1. Relative to the control intervention, patients who use VR will report meaningfully reduced pain scores, will require less pain medication (opioid equivalents, and non-opioids), will report fewer opioid complications (e.g., nausea, vomiting, constipation), and will delay requests for breakthrough doses of pain medication.
2. Compared to controls, patients who use VR in the hospital will stay in the hospital for less time, report greater satisfaction with care, and will experience fewer readmissions.
3. Compared to controls, patients who use VR will report greater satisfaction with care, as measured by HCAHPS scores after 6 weeks of patient discharge

Exploratory aim:

1. Assess for reduction in cortisol levels with use of VR

Study Procedures:

Overview and Study Design

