criteria. However, preliminary analysis on patients enrolled in the study from 1 October 2016 to 30 September 2017 indicate that patients with higher baseline pain intensity experience greater reductions in pain as a result of VR when compared to the control group. Upon several subgroup analyses and communications with Cedars-Sinai providers, we determined a change in focus of diagnosis would improve the power of these analyses. The Cedars-Sinai Orthopedic Department has a large and steady supply of high severity pain patients that might benefit from a pain distraction intervention. The department's physicians have also expressed a strong interest in alternative pain treatment modalities and would like to explore these distraction methods further. We will use the existing protocol to continue to recruit only hospitalized orthopedic patients for a full cohort of 160 orthopedic patients for this trial. Because our currently enrolled sample (1 October 2016 to 30 September 2017) already includes some orthopedic patients, we will recruit only additional orthopedic patients until we complete the cohort of 160 orthopedic patients, accounting for possible withdrawal from the study. Once this cohort of patients is complete, the overall sample size for the entire study including patients from all diagnosis groups will be up to 244 patients.

Eligibility Criteria

The following criteria will be used to define patient eligibility:

Inclusion Criteria:

- Able to understand the goals of the study and provide informed consent
- Until 30 September 2017, any hospitalized patient under care of CSMC inpatient service (ISP), gastroenterology, or psychiatry, admitted between 1 October 2016 and 30 September 2017, who is not excluded due to criteria listed below.
- From 1 October 2017 Until 30 September 2018, any hospitalized patient under the care of CSMC orthopedic providers
- At least 18 years of age
- English speaking

Exclusion Criteria:

- Unable to consent to study due to cognitive difficulty
- Current diagnosis of epilepsy, dementia, or other neurological disease that may prevent use of VR hardware and software
- Sensitivity to flashing light or motion
- Pregnancy, or a medical condition where the patient is prone to frequent nausea or dizziness
- Recent stroke
- Post-transplant patient, or pre-transplant patient with severe illness
- Patient on ventilator, BiPAP, or other breathing assistance equipment

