response rate of approximately 25%. We will use these data to estimate changes in satisfaction associated with exposure to the intervention condition, versus the control condition. The HCAHPS survey has demonstrated face validity in previous studies.²⁸

Salivary cortisol assay (OPTIONAL):

The salivary cortisol assay will be processed at the lab at CSMC which is then shipped to Quest Diagnostics. It is stable at room temperature for 5 days. The assay is performed using liquid chromatography/tandem mass spectrometry. While cortisol has a diurnal variability with levels highest in the early morning, we will be assessing percent change of cortisol levels over the 10 minutes of the VR demonstration or Health and Wellness channel viewing in each individual. This will minimize the effect of the diurnal variation.

Data Collection

We will collect the following information about VR intervention and Control participants:

- Name and Medical Record Number (secured and stored separate from all other data below)
- Age
- Sex
- Race/Ethnicity
- Admitting Diagnosis during inpatient stay
- ISP ward
- Previous diagnoses of epilepsy and other neurological or visual impairments.
- All Pain ratings throughout the hospital stay.
- All opioid and non-opioid pain medication usage information (dosage amount and timing).
- HCAHPS Patient Satisfaction Picker Survey responses.

Demographic and descriptive clinical data will be abstracted by [name] or authorized study staff at the time of patient selection, and vital signs will be collected before and after the intervention.

Analysis Plan:

The current study plan allows us to enroll an average of three patients per week at a minimum.

We will calculate descriptive statistics for patients in each group. We will then perform bivariate analyses to compare mean cumulative pain scores, morphine milligram equivalents, and average length of stay between groups using t-tests. We will compare the proportion with an opioid complication between groups using chi-squared, and calculate the “number needed to treat” in order to prevent one additional complication with VR vs. no usual care. We will then perform multivariable linear regression analysis to predict pain scores while controlling covariates, including age, demographics, comorbidities, and baseline pain scores. We will report both intention-to-treat analyses including all evaluable patients

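### No time origin is set for length of stay or opioid complications although patients join mid-admission; counting from randomisation would give more precise tests and a clearer complication effect

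*Combined protocol and SAP*

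**What the plan says.** The Analysis Plan compares "morphine milligram equivalents, and average length of stay between groups using t-tests". For complications it states "We will compare the proportion with an opioid complication between groups using chi-squared", and it then derives an NNT "in order to prevent one additional complication with VR vs. no usual care". None of these sentences says when counting starts. The multivariable regression described next is for pain scores only, so neither outcome has a planned adjustment.

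Both outcomes serve stated hypotheses. Under Specific Aims and Hypotheses, VR patients "will report fewer opioid complications (e.g., nausea, vomiting, constipation"), and "patients who use VR in the hospital will stay in the hospital for less time". The bracketed examples are the only definition of a complication in the document.

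On entry, the second-phase inclusion criterion reads "From 1 October 2017 Until 30 September 2018, any hospitalized patient under the care of CSMC orthopedic providers". Neither the eligibility criteria nor Patient Recruitment and Study Procedures limits the time since admission. A patient is referred, shows interest, consents and receives the allocated intervention, with use continuing for up to 20 days of the stay.

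Whole-stay collection is stated for pain ("All Pain ratings throughout the hospital stay", under Data Collection) and, under Post-Intervention Procedures, for pain ratings and medication history. The Data Collection list does not contain opioid complications, nor times of admission, randomisation or discharge.

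**The concern.** VR can act only after allocation. A patient randomised on day 4 has days already spent in hospital, and may already have had opioid-related vomiting or constipation, whichever arm follows. If those days and events enter the endpoints, they carry no information about VR.

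For length of stay, the loss is precision and a smaller relative reduction. For a yes/no complication endpoint, patients already counted as having the event cannot be seen to benefit, so the two proportions rise together, the risk ratio moves towards 1 and the chi-squared test weakens.

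Leaving the window open also means that it could be chosen after the data have been seen.

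**Working it through.** **The plan's own figures.** The plan gives no SD, event rate, effect size or power for length of stay or complications, so there is nothing of its own to reproduce for them. Its between-group figure is for pain: 0.52 SD with 80 per group, at 5% alpha and 80% power. A two-sided calculation on those inputs gives 59 per group, and 80 per group gives about 90% power. Below, 0.52 SD is borrowed only as a yardstick. The group sizes are 80 (orthopaedic cohort) and 122 (whole trial).

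**Length of stay.** Write whole stay = pre + post, where pre is days before randomisation.

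- Mean difference: randomisation gives pre the same expectation in both arms, so the expected difference in whole stay equals that in post. There is no bias in days.
- Variance, if pre and post are independent: SD_post² + SD_pre². With SD_post = 3 (assumed), the ratio to the post-only variance is 1 + SD_pre²/9.
- Standardised effect: 0.52/√ratio. Power is from a two-sided two-sample t-test at 5%.

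| SD_pre (assumed) | Variance ratio | Effect in SD | Power, 80 per group | Power, 122 per group |
|---|---|---|---|---|
| 0 (post only) | 1.00 | 0.52 | 90% | 98% |
| 1 day | 1.11 | 0.49 | 87% | 97% |
| 2 days | 1.44 | 0.43 | 78% | 92% |
| 3 days | 2.00 | 0.37 | 64% | 82% |

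A simulation with 122 per arm illustrates the relative reduction. It assumed a mean of 2 days before randomisation and 4 versus 3 days after. The difference was 1.00 day under both definitions. The standard error rose from 0.34 to 0.42, and the relative reduction fell from 1/4 = 25% to 1/6 = 17%.

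**Opioid complications.** Assume that 20% of patients have a complication before randomisation, and that new onset among the other 80% is 37.5% on control and 18.75% on VR.

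- Whole-stay count: 0.20 + 0.80 × 0.375 = 50% versus 0.20 + 0.80 × 0.1875 = 35%. Risk ratio 0.70, risk difference 15 points, NNT 1/0.15 = 6.7.
- New-onset count over all randomised patients: 0.80 × 0.375 = 30% versus 0.80 × 0.1875 = 15%. Risk ratio 0.50, risk difference 15 points, NNT 6.7.
- Power (two proportions, two-sided 5%, 122 per group): about 66% for 50% versus 35%, and about 80% for 30% versus 15%. With 80 per group: about 48% and 62%.

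The risk difference and NNT are the same under both counts. The risk ratio and the power are not.

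**The case against.** Three stronger readings are tempting, and the documents support none of them.

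First, a reader might infer that the plan counts complications over the whole admission. It does not say so: whole-stay collection is stated for pain ratings and medication history, and counting complications from enrolment fits the text equally well. For length of stay, admission to discharge is the ordinary meaning, but it too is unstated. The defect is an undefined window, not a wrong one.

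Second, one might say that the length-of-stay effect is diluted. In days it is not, because pre-randomisation days balance in expectation. Only precision, the standardised effect and the relative reduction suffer.

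Third, one might say that the NNT would be too large. In the scenario above it is 6.7 under both counts. An NNT of 1/0.1875 = 5.3 appears only if the 20% already affected are dropped from the denominator, which departs from the stated intention-to-treat set of all evaluable patients as allocated. The NNT would be inflated under a different assumption, that patients with an earlier complication keep the same later risk. With later risks of 30% versus 15% for everyone and 20% prior, the whole-stay difference is 0.80 × 15 = 12 points and the NNT 8.3, against 6.7. The documents give no basis for choosing between these assumptions.

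It is also fair to say that the sample size is justified on pain scores alone, so no power claim for these outcomes is broken, and that at 122 per group length-of-stay power stays above 80% throughout the assumed range. Both points limit the size of the problem. Neither supplies the missing definition.

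**Conclusion.** The concern holds as a gap in definition with a cost in precision. Patients can enter mid-admission, two outcomes tied to stated hypotheses have no time origin, and the length-of-stay t-test is unadjusted. Under the ordinary meaning of length of stay, the treatment difference in days remains valid but is estimated less precisely. How much less depends on the spread of days before randomisation: across the assumed range the loss runs from about 3 to 27 percentage points of power at 80 per group (90% to 87% or 64%), and from about 1 to 16 at 122 (98% to 97% or 82%). For complications, the consequence is conditional on events present at entry being counted. It is then a risk ratio nearer 1 and a weaker test.

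All sizes rest on assumed SDs, independence of pre- and post-randomisation days, an effect borrowed from pain scores, and assumed complication rates. The direction of the precision loss needs only that pre-randomisation days vary and are not strongly negatively correlated with later days. This should be settled before analysis, but it does not invalidate the comparison.

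**What to change.** - Define length of stay as time from randomisation to discharge, and adjust for days already spent in hospital. Report whole-admission stay descriptively.
- Define the complication endpoint as an opioid complication with onset after randomisation, listing the qualifying events. Keep all randomised patients in the denominator, to match the intention-to-treat set, and compute the chi-squared test and the NNT on that basis.
- Record whether a complication is present at randomisation as a baseline variable.
- Add to the Data Collection list the complications, their source and onset time, and the times of admission, randomisation and discharge.

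The length-of-stay change costs little beyond wording and three time points. The complication change costs more: complications are not on the current list, so they need a working definition and extra chart abstraction, including onset times.

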by randomized allocation, and per-protocol analyses limited to just those patients in the intervention arm who opt to use VR (while accounting for dose-response potential). We will adopt a P-value of <0.05 as evidence for statistical significance, and calculate 95% confidence intervals around point estimates. All analyses will be performed using Stata for Windows (StataCorp, College Station, TX).

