We have powered this study based on our previous research on pain management with VR¹⁸⁻²⁰, which reported clinically meaningful shifts of approximately 1 SD in self-reported pain scores following brief exposure to VR. Several previous studies²¹⁻²³ have established that the minimal clinically important difference on patient-reported pain rating scales (visual analog or numerical ratings) is approximately 13% (approximately 1.4 points on a 0-10 scale, with a standard deviation of 14%). Thus, we are interested in measuring a 1SD change in pain ratings following exposure to the VR intervention, but we will collect a sufficiently large sample to measure smaller changes both within patients exposed to VR, and in comparison to a control group. For all analyses, we will assume a 5% Type I error rate (alpha) and a 20% type II error rate (or 80% power). For **within group analyses**, we would require a minimum of 10 patients to detect a 1 SD change in pain scores. However, we have powered the study to detect a 0.38 SD difference **within each group** (with 58 patients per group), however have modified this to 80 patients per group. We used this method to calculate and justify the required sample size for a complete cohort of orthopedic patients. Therefore, the overall intervention and control groups, along with the orthopedic subgroup will be adequately powered for analysis. The sample-size modification is required due to over-estimation of adherence, and aims to support a "per-protocol" analyses. We plan on conducting this per protocol analysis among treatment-compliant subjects *in addition* to the intent to treat analysis. The additional subjects, then, will bring the total N of the per-protocol analysis into a range capable of detecting the hypothesized effect-size used in the original sample-size calculation. While sample-size re-estimation based on observed difference with a limited number of subjects may be biased and misleading, we feel that the goal of the trial (determining efficacy rather than effectiveness) - coupled with the fact that randomization procedures will remain unchanged - supports the request.

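### Intention-to-treat and per-protocol analyses share one P<0.05 rule with neither named primary, and the per-protocol set is formed after randomization with no use threshold or comparator

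*Combined protocol and SAP*

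**What the plan says.** The Analysis Plan lists t-tests on pain scores and other outcomes, then a linear regression for pain with covariates that include baseline pain. It then sets two analyses side by side: "We will report both intention-to-treat analyses including all evaluable patients", grouped as randomized, and "per-protocol analyses limited to just those patients in the intervention arm who opt to use VR (while accounting for dose-response potential". A single rule follows: "We will adopt a P-value of <0.05 as evidence for statistical significance". Nothing is labelled primary, and the word evaluable is not defined.

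The sample-size paragraphs of the same section explain the rise from 58 to 80 per group. "The sample-size modification is required due to over-estimation of adherence", they say, and the added patients are meant to support the per-protocol analysis. "We plan on conducting this per protocol analysis among treatment-compliant subjects", in addition to intention-to-treat. The plan concedes that "sample-size re-estimation based on observed difference with a limited number of subjects may be biased and misleading", but relies on "the goal of the trial (determining efficacy rather than effectiveness" and adds "coupled with the fact that randomization procedures will remain unchanged". The between-group paragraph then compares everyone exposed to VR with an 80-patient control group at 0.52 SD, without saying which analysis set that is.

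Who uses VR is settled after allocation. Under Overview and Study Design, use beyond the 10-minute trial run depends on the patient's interest. Under Experimental Group, Pre-Intervention Procedures, the headset is left in the room only if the test run also passes without adverse effects. Under VR/TV Usage Monitoring, patients in both arms log their own use, and reporting error is admitted.

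**The concern.** If the two analyses disagree, the plan does not say which one decides whether VR works. That matters because a per-protocol set built on interest and tolerability is no longer a randomized group, and the listed covariates (age, demographics, comorbidities, baseline pain) do not cover either trait. An efficacy goal does not cure this: an efficacy estimate still needs comparable groups. Unchanged randomization protects the comparison of whole arms, not of a subset chosen afterwards. More patients narrow the interval around a biased estimate without moving it.

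Without a use threshold or a comparator, the set could also be settled after results are known. The deciding population is open too: the plan describes an orthopedic cohort of 160 and an overall sample of up to 244, and calls both adequately powered.

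**Working it through.** **1. The plan's own figures.** Inputs from the Analysis Plan: alpha 5%, power 80%, 0.52 SD between groups, 80 per group. Sidedness is not stated; two-sided is taken.

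n per group = 2 × (1.960 + 0.842)² / 0.52² = 58.05, so 59 (60 with the t distribution).

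The stated 80 is not reproduced at 80% power. At 80 per group, power for 0.52 SD is 90.5%; at 58 it is 79%. So 0.52 SD matches the old sample size. The within-group figure (0.38 SD, 58 patients) is close: a paired t-test needs 57. The ratio 58/80 = 0.725 would fit an assumed 72.5% use, but 0.52 SD at 90% power also needs 79 per group. The documents give no use rate.

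**2. Readings of the per-protocol analysis that fit the text.**
- VR users against all controls: only the VR arm is restricted.
- Compliers in both arms: the sample-size text names no arm, both groups rise to 80, and both arms keep logs.
- A within-arm or dose-response analysis: the set is limited to VR-arm patients, and the rise from 58 to 80 sits in the within-group sentence.

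Each relies on behaviour after randomization.

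**3. Size under the first reading only.** Assumed: no VR effect, 80 per arm, total SD 1, no adjustment, and a prognostic gap between users and non-users.

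Bias = (1 − use) × gap; z = bias / √(1/(80 × use) + 1/80); two-sided error = Φ(z − 1.96) + Φ(−z − 1.96).

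Example, 50% use and 0.5 SD gap: bias 0.25, z = 0.25 / √(1/40 + 1/80) = 1.291, error 25.2%.

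| Assumed use | Gap 0.2 SD | Gap 0.5 SD |
|---|---|---|
| 50% | 8.1% | 25.2% |
| 72.5% | 6.2% | 12.5% |
| 90% | 5.2% | 6.1% |

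A simulation of 12,000 trials per cell agrees to within 0.6 percentage points. With adjustment for baseline pain (8,000 simulated trials, 72.5% use, baseline correlation 0.3 to 0.6, same gaps), the error is 4.7% to 5.1% if baseline pain carries the whole gap and 6.5% to 16.7% if it carries none.

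**4. What intention-to-treat can detect.** The detectable difference at 80% power (two-sample t, unadjusted) is 0.446 SD at 80 per arm and 0.360 SD at 122. If 0.52 SD applies to users only and non-users gain nothing, the intention-to-treat effect is 0.52 × use:

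| Assumed use | Effect (SD) | Power, 80 per arm | Power, 122 per arm |
|---|---|---|---|
| 50% | 0.260 | 37% | 53% |
| 60% | 0.312 | 50% | 68% |
| 72.5% | 0.377 | 66% | 83% |
| 90% | 0.468 | 84% | 95% |

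If non-users gain the full effect, for example from the trial run, power is 90% and 98%. Baseline adjustment raises power: the 66% becomes 70% at a correlation of 0.3 and 84% at 0.6, from effect / √(1 − r²).

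**The case against.** The text leans towards intention-to-treat. It is listed first, per-protocol is described as additional, and Study Population and Period uses exposed for the whole arm of 122, so the 0.52 SD comparison may well be between randomized arms. All of this stands. A reader might infer that per-protocol is the intended main analysis; the documents do not say so. But a lean is not a rule, and the efficacy goal and the reason given for the larger sample pull the other way.

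A reader might also infer that the two descriptions of the set contradict each other. They do not have to: patients who opt to use VR and treatment-compliant patients can be the same people. The set is under-specified rather than contradictory.

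The type I figures can fairly be called assumed. They apply to one of three readings, and 25% needs both the lowest use and the largest gap; at 90% use the error is 5% to 6%. The planned covariate adjustment could remove most of the bias if baseline pain drives the choice. None of this supplies the missing hierarchy, threshold or comparator, which rest on no assumption.

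**Conclusion.** The point holds, and should be fixed. What is certain from the text is that two analyses share one significance rule without a stated order, and that one of them uses an undefined set selected after randomization. The 5% to 25% error range is an illustration, conditional on the users-against-all-controls reading and on assumed use and gap.

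Three stronger inferences are not supported. First, that the bias favours VR: its direction is unknown, giving false benefit if users would have had less pain anyway and false harm if more. Second, that actual use was 72.5%: that is back-calculated from 58/80, and another explanation fits equally well. Third, that the larger sample serves only the per-protocol analysis: it also lowers the detectable intention-to-treat difference, from 0.52 SD at 58 per arm to 0.45 SD at 80.

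**What to change.** In the Analysis Plan and its sample-size paragraphs:

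- State that the intention-to-treat comparison of pain scores by randomized arm, adjusted for baseline pain as already planned, is primary and the sole basis for the efficacy claim. Per-protocol and dose-response analyses are supportive only.
- Name the one population in which it decides: the 160 orthopedic patients or all 244. The choice is the sponsor's.
- Before analysis, define the per-protocol set by a stated amount of use and name its comparator, noting that use is self-logged with admitted reporting error.
- Define evaluable without reference to VR or TV use.
- Restate power for intention-to-treat, giving the detectable difference for the chosen population. If 0.52 SD is meant for users only, show power over a range of use rates, as in the table above, rather than at one assumed rate.

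The cost is wording and a restated power calculation, with no new data and no added enrolment. The downside is that non-use may dilute the intention-to-treat effect, so the stated power may be less favourable than the present text suggests.

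### The plan powers a pre-post change within each arm and cites that method for the orthopedic cohort, although a decline common to both arms could make such a test significant with no VR effect

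*Combined protocol and SAP*

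**What the plan says.** The power paragraphs of the Analysis Plan set two goals for the pain data: "to measure smaller changes both within patients exposed to VR, and in comparison to a control group". One pair of error rates is meant to serve every analysis: "we will assume a 5% Type I error rate (alpha) and a 20% type II error rate (or 80% power".

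The within-group part comes first. It says "we would require a minimum of 10 patients to detect a 1 SD change in pain scores", then "we have powered the study to detect a 0.38 SD difference". That target is stated separately for the VR and control arms, and the numbers behind it are given as "with 58 patients per group), however have modified this to 80 patients per group". The next sentence reads "We used this method to calculate and justify the required sample size for a complete cohort of orthopedic patients", after which the plan concludes that the two groups and the orthopedic subgroup are adequately powered. The step from 58 to 80 has its own explanation: "The sample-size modification is required due to over-estimation of adherence", with the aim of supporting a per-protocol analysis.

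The between-group part follows. It gives 80 per group as the number required to detect a difference of 0.52 SD between VR and control.

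Earlier in the Analysis Plan, the listed pain analyses are t-tests between groups and a multivariable regression with baseline pain among the covariates. No pre-post test is listed. The significance rule is general: "We will adopt a P-value of <0.05 as evidence for statistical significance".

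**The concern.** A change within one arm has no control. Inpatient pain moves with recovery and with analgesics. If VR is taken up when pain is high, pain also moves by regression to the mean. The study gives VR for breakthrough pain, and the second phase was directed to orthopedic patients because they tend to have severe pain. Both features make regression to the mean plausible.

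The plan nonetheless gives this contrast its own error rates, effect size and sample size, and cites it for the orthopedic cohort before any between-group figure appears. It does not label within-arm results as descriptive, and the 0.05 rule is not restricted to between-arm contrasts. The trial could therefore report a significant fall in pain with VR that the television arm shows equally.

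**Working it through.** **Inputs from the Analysis Plan.** Alpha 0.05 and power 0.80; within-group effects of 1 SD (n = 10) and 0.38 SD (n = 58, then 80); between-group effect of 0.52 SD with 80 per group. The power text does not state sidedness; two-sided is assumed.

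**1. Reproduce the within-group figures.** For a paired (one-sample) t-test, power = P(T > t[0.975, n−1]), where T is noncentral t with n−1 degrees of freedom and noncentrality d√n.
- d = 1: n = 9 gives 74.8% and n = 10 gives 80.3%, so the required n is 10. The plan says 10.
- d = 0.38: n = 56 gives 79.8% and n = 57 gives 80.5%, so the required n is 57. The plan's 58 gives 81.2%.

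Both reproduce, so these are pre-post calculations, in SD units of the change score. At n = 80 the same test has 91.9% power for 0.38 SD.

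**2. What that test does when VR has no effect.** Assume a mean decline δ, in SDs of the change score, that is equal in both arms. The documents give no value for δ, so a range is shown. With n = 80 the noncentrality is δ√80 = 8.944δ and the critical value is t[0.975, 79] = 1.990.

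| Assumed common decline δ | δ√80 | P(significant decline in VR arm) |
|---|---|---|
| 0.1 SD | 0.89 | 14% |
| 0.2 SD | 1.79 | 42% |
| 0.3 SD | 2.68 | 76% |
| 0.4 SD | 3.58 | 94% |
| 0.5 SD | 4.47 | 99% |

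With δ = 0 the corresponding figure is 2.5%, the lower half of the two-sided 5%.

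In the between-arm comparison δ cancels. In a simulation of 20,000 trials with 80 per arm, the two-sample t-test was significant in 5.1% of trials both at δ = 0.2 and at δ = 0.38.

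**3. Does 80 per arm stand on the between-arm contrast?** For a two-sample t-test the noncentrality is d√(n/2), with 2n−2 degrees of freedom.
- 0.52 SD at 80% power: the normal approximation is 2(1.960 + 0.842)²/0.52² = 58.1, so 59. With the t distribution, n = 59 gives 79.98% and n = 60 gives 80.6%, so 60.
- 0.52 SD with 80 per group: noncentrality 0.52√40 = 3.29, power 90.5%.
- 80 per group at 80% power: detectable difference 0.446 SD.
- With baseline adjustment, if baseline and outcome correlate 0.5 (assumption): 0.446 × √(1 − 0.25) = 0.386, about 0.39 SD.
- 0.52 SD with 58 per group: 79.3% (t) or 80.0% (normal). The 0.52 therefore looks carried over from the former 58 per group.

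So 80 per group is more than enough for 0.52 SD in complete data, but the stated combination of 0.52 SD, 80 per group and 80% power does not agree with itself.

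**The case against.** The best defence is that the trial is already set up to be judged between arms. The first hypothesis is worded relative to control. The Overview plans to compare pre-post changes between the two groups. The Control Group section says the evaluation remains a between-subjects comparison. The listed pain tests are between-group, with a regression that includes baseline pain. All of this stands, and it means that much of the remedy is already in the plan.

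The defence also disposes of four stronger readings that a reader might infer.

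- *That the orthopedic sample size rests only on a pre-post test.* The sentence citing the method does follow the within-group figures. However, a between-group calculation is given for the same 80 per group, and the step from 58 to 80 is attributed to adherence.
- *That a significant VR-arm change will be taken as the efficacy result.* The plan nowhere says so. It leaves the role of the within-arm tests unstated.
- *That those tests are bound to be positive.* This depends on a decline the documents do not quantify. At 0.1 SD the chance is only 14%. The power text refers to brief exposure and a 20-minute period, which leaves little time for healing, and eligibility sets no minimum pain score. Against that, pain scores are taken from the health record as charted, so the interval is not fixed.
- *That the cohort is underpowered, because 0.38 SD between groups would need 110 per group and 80 gives 66.6%.* The plan states 0.38 SD only as a within-group change, and its between-group target is 0.52 SD.

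What the defence does not answer is that an analysis with its own power statement has no stated method, role or limit, and that it is cited as justification for a cohort in a randomised comparison.

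**Conclusion.** The point holds as one of justification and reporting. It is not a flaw in the number of patients or in the listed pain analyses. The within-group calculation reproduces but answers a question that cannot be attributed to VR. With 80 patients and no VR effect, the chance of a significant VR-arm decline runs from 14% to 99% as the assumed common decline goes from 0.1 to 0.5 SD, against about 5% for the between-arm test. Because that decline is an assumption, the supported statement is that the test could be positive from natural course alone, not that it would be.

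The 80 per arm stands on the between-arm contrast, at about 90% power for 0.52 SD in complete data, although the plan's own figure for that contrast needs correcting. These results assume two-sided tests and approximately normal scores. The change is worth making because it costs little and closes off a misleading claim.

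**What to change.** 1. State that within-arm pre-post changes in pain are descriptive: means and intervals by arm, without P-values.
2. State that every claim about pain rests on the between-arm difference adjusted for baseline pain, which the Analysis Plan already lists as a covariate.
3. Replace the within-group justification of the orthopedic cohort with a between-arm one: 80 per arm with complete data detects 0.446 SD at 80% power, or 0.52 SD at about 90%. If the benefit of adjustment is quoted, give about 0.39 SD and label the baseline correlation of 0.5 as an assumption.
4. Correct the statement that 0.52 SD requires 80 per group; at 80% power it needs about 60. If the difference is an allowance for non-adherence, give the rate used. The step from 58 to 80 would correspond to 58/80 = 72.5% adherence, a figure the plan does not state.

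The cost is a revision of wording, with no new patients or data. The 0.38 SD within-group power claim is lost.
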